AAT/tDCS sessions of personal combined-cue exposure, with follow-up assessments of cig/day, intent and confidence to quit at 1 week and 1-month post-training.

Our specific goals are:

Aim 1: Determine the effectiveness of AAT and tDCS to attenuate cue-induced

craving and attentional bias to personal smoking stimuli. AAT, tDCS, and combined AAT + tDCS will each lead to greater reductions in pre-post training cue-induced craving and improved behavioral (quicker reaction time) and neurophysiological (lower P300 ERP) measures of attentional bias for smoking cues over the control condition.

Aim 2: Determine the effectiveness of AAT and tDCS to reduce cue-provoked smoking behavior and daily smoking, and to increase intent and confidence to quit. AAT, tDCS, and combined AAT + tDCS will

each lead to greater pre-post-training reductions in smoking topography measures (latency to light & puff volume) assessed during cue exposure, as well as reduced cigs/day and increased confidence and intent to quit from pre-training to post-training and 1-week & 1-month follow-up over the control condition.

Aim 3: Examine if changes in reactivity to smoking-related cues (Aim 1) are associated with posttraining reductions in smoking topography and/or cig/day and increases in intent and confidence to quit. (Aim 2). Reduced craving and attentional bias to smoking stimuli across all groups will be associated with reductions in smoking topography post-training, as well as post-training and follow-up changes in cigs/day and confidence and intent to quit Secondary Aim: Explore sex and other individual differences as moderators of outcome measures to explore who might benefit most from AAT and tDCS methods.

There have been few recent innovative approaches for alleviating cue-induced craving to smoke. AAT and tDCS are two promising methods to newly apply to this endeavor. Although this exploratory work is not fully powered to detect significant interaction effects of AAT and tDCS, we will examine the size of the interaction to inform potential efficacy trials of combined AAT + tDCS vs the individual therapies alone. The results here will thus guide a future RCT of novel CET methodology within a cessation trial aimed at helping more smokers stay quit.

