The proposed study will be the first active and sham-controlled test of AAT and tDCS during personalized multi-cue exposure to attenuate several indices of smoking-related cue reactivity and behavior. Several aspects of this exploratory/developmental study are highly innovative. 1) AAT: Although recommended, AAT effects on cue-induced craving have surprisingly not been formally studied. Past AAT smoking cue studies reveal promising effects for AAT on measures of daily smoking and attentional bias, but have not examined cue-induced craving. Likewise, no AAT studies have included neuropsychological measurement of attentional bias (EEG) or changes in cue-induced smoking topography (latency to light, puff volume). 2) tDCS: tDCS applied to the dlPFC can reduce reactivity to proximal smoking cues (cigarettes, lighters) and can reduce daily smoking in non-quitting smokers. This will be the first assessment of dlPFC-targeted tDCS effects on smoking attentional bias (Stroop and EEG), craving to personal cues, and cue-induced smoking topography. 3) Combining AAT + tDCS: No studies have examined combined AAT+tDCS on smoking CR, attentional measures or smoking behavior. Given that tDCS is known to be more effective when used while engaging the faculty targeted for change we anticipate combined AAT+ tDCS targeting dlPFC will have a synergistic effect on our comprehensive index of reactivity measures to combined personal smoking cues, as well as daily smoking and intent and confidence to quit. Our 2 x 2 design allows us to examine AAT and tDCS independently across multiple new outcome variables, as well as the combined impact of these two methods. 4) Multiple Personal Cues Exposure: CET should be most effective when cues evoke smokers' strongest reactivity and capture key elements of the original contexts of learning. The proposed study will be the first to incorporate all cue types (people, places and objects) during CET to target numerous specific stimuli that trigger each smoker's strongest urges to smoke. Multiple exposures to real world cue re-creations should enhance the generalizability of training outside of sessions, a purported shortcoming of past CETs, and allow us to capture smokers' most salient cues without the inherent difficulties of conducting real world exposures.

Study Design

1. Total number of subjects to be enrolled at this site (enter -1 for chart reviews, banking, registries):

160

2. Describe and explain the study design:

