*** Identify the subgroups and provide a justification:**

Children, individuals defined as under the age of 18, will not be included as it is illegal to sell cigarettes to minors in Pennsylvania. The safety and efficacy of tDCS has not been tested in pediatric smokers, and standard doses have not been established.

8. Describe the power analysis used and cite your method of statistical analysis.

If a power analysis is not possible, thoroughly justify the sample size required for the study, including appropriate literature citation (alternatively provide page reference in attached protocol):

Statistical design and power

This study uses a 2 x 2 AAT (AAT, active control[AC]) x tDCS (tDCS, sham tDCS) design to assess prepost training changes in cue-induced craving and smoking

topography (latency to light and puff volume during cue exposure) and attentional bias (reaction time and ERPs) to smoking-related cues, as well as daily smoking (cigarettes per day) and confidence and intent to quit. The primary analyses (Aims 1 and 2) will be evaluated via repeated measures multivariate analysis of covariance (RM-ANCOVA) and will test the main effects of AAT, tDCS, and their interaction on measures of craving, reaction time, P300 amplitude, controlling for baseline levels as covariates (Aim 1). This process will be repeated for Aim 2, where MANCOVA will test effects on latency to smoke, total puff volume, and cigs/day. An additional 2x2x3 repeated measures (RM-) MANCOVA will test group differences in cig/day and intent & confidence to quit

across time points (post-training, 1-week, and 1-month). For Aim 3, regression analysis will be used to examine if attenuation of cue-induced craving and attentional bias measures predict reductions in smoking topography and daily smoking and elevations in intention to quit and confidence to quit, while controlling for baseline levels of these variables. Exploratory analyses will probe whether sex and other individual differences (e.g., age, FTND) moderate the effects of AAT/tDCS training on all outcome variables.

Power is based on n=20 high treatment-interest smokers per group, with 4 experimental groups. Drop outs

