*** Describe the circumstances and any procedures for orderly termination:**
It is possible that the subject may be removed from the research study by the researchers if he/she is unable to perform any of the required tasks or does not show up for scheduled study visits. He/She will always be paid for a session she attended prior to being formally withdrawn from the study.

8. Describe procedures that will be followed when subjects withdraw from the research, including partial withdrawal from procedures with continued data collection and data already collected:

Research data will be kept and reviewed for an indefinite period of time. Research information collected before excusal or withdrawal from the study will continue to be used and disclosed by the investigators for the purposes described above.

Placebo Arm

1. * Is there a commonly used diagnostic/treatment approach that is currently recognized as being effective for the proposed subjects' disease or condition, and that will be withheld from subjects assigned to the placebo arm of this research study:

N/A - the proposed subjects are normal, healthy volunteers

2. Describe the commonly used diagnostic/treatment approaches that will be withheld from subjects assigned to the placebo arm of this research study:

3. Is enrollment into this study limited to individuals in whom the commonly used diagnostic/treatment approaches are known to be ineffective or intolerable?

4. Provide a scientific justification for the placebo-control arm of this research study:

This is a balanced 2 x 2 design to examine the impact of two new methods to reduce cue reactivity to personal smoking cues. The placebo arm allows us to examine the individual and combined impact of the two techniques and compare them with a time and contact control. The effectiveness of the techniques being examined, independently or in combination, as methods to reduce cue reactivity to personal smoking cues has yet to be examined, so a placebo comparison is warranted.

5. How long will subjects participate in the placebo arm? Justify why this duration is necessary:

They will be in the placebo arm for the duration of the study 10 sessions. There are also follow-up phone calls at 1 week and 1 month post-training. This allows the placebo arm to serve as a control for subject time and contact.

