6. How frequently will the subject's condition or disease be monitored and compare that to the frequency of monitoring associated with standard care for this disease/condition?

7. What specific endpoints will result in discontinuing a subject's participation due to worsening of the subject's disease or condition?

8. What is the risk to subjects who receive no active treatment for their disease or condition while in the placebo arm?

There is no notable risk, their smoking behavior and craving is expected to remain stable, whereas we anticipate possible reductions in these measures in the other arms of the study.

9. Describe the planned involvement of a 'contact person' who interacts with the subject on a regular basis and who will notify the investigators immediately of any problems related to the subject's disease or condition:

Note: The involvement of the contact person must also be addressed in the consent form

Conflict of Interest

Institutional Financial Interests

1. * To the best of your knowledge, has the University of Pittsburgh optioned or licensed technology that will be tested or evaluated in this research?

Yes No

Ancillary Reviews

1. Ancillary reviews or notifications selected below are required based on previous answers to questions. If a selection is incorrect, return to the appropriate page and adjust the answers to questions on that page:

- Conflict of Interest (**COI**)
- Clinical and Translational Research Center (**CTRC**)
- Data Security
- Honest Broker
- UPMC Investigational Drug Service
- Pitt Medical School Review
- Pitt+Me
- IND & IDE Support(**IIS**)
- Radioactive Drug Research Committee (**RDRC**)(study involves the evaluation or use of procedures that emit ionizing radiation)
- ORP Business **Manager** (required for industry sponsored studies)
- Religious Directives
- Scientific Review
- Health Record Research Request (**R3**) (required if using UPMC clinical data and authorization for other UPMC data sources for research)
- UPMC Office of Sponsored Programs and Research **Support** (using UPMC facilities and/or UPMC patients during the conduct of the study)

2. Additional ancillary reviews the PI may choose to include as needed for the research:

- Human Stem Cell Oversight (**hSCRO**)
- Institutional Biosafety Committee (**IBC**)(study involves deliberate transfer of recombinant or synthetic nucleic acid molecules)

Good Clinical Practice (GCP) Training

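### Aims 1 and 2 claim that AAT+tDCS beats the control condition, but no prespecified test makes that comparison; separately, the sex and age strata are not named in the primary models

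*Combined protocol and SAP*

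**What the plan says.** **Aims.** Study Aims, item 1 states for Aim 1 that "AAT, tDCS, and combined AAT + tDCS will each lead to greater reductions in pre-post training cue-induced craving", and the comparator closes that sentence: "measures of attentional bias for smoking cues over the control condition". Aim 2 makes the same three-part claim for topography, daily smoking and quit measures, ending "increased confidence and intent to quit from pre-training to post-training and 1-week & 1-month follow-up over the control condition".

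**Control arm.** Placebo Arm, item 4 justifies this arm because it "allows us to examine the individual and combined impact of the two techniques and compare them with a time and contact control".

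**Analysis.** Study Design, item 8 says the Aim 1 model "will test the main effects of AAT, tDCS, and their interaction on measures of craving, reaction time, P300 amplitude, controlling for baseline levels as covariates". The process is repeated for Aim 2 (latency, puff volume, cigarettes per day). A 2x2x3 repeated-measures model then looks at group differences in cigarettes per day, intent and confidence over three time points, with no contrast named. Study Aims, item 1 adds that "we will examine the size of the interaction to inform potential efficacy trials of combined AAT + tDCS vs the individual therapies alone".

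**Meaning of AAT and tDCS in the aims.** The Innovation text (Study Aims, item 2) says the 2 x 2 "design allows us to examine AAT and tDCS independently across multiple new outcome variables, as well as the combined impact", which suggests factors. Placebo Arm, item 8 says of control participants that "their smoking behavior and craving is expected to remain stable, whereas we anticipate possible reductions in these measures in the other arms of the study", which suggests separate arms.

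**Strata.** Study Design, item 2 stratifies randomisation by sex and age. In item 8 the primary models name only baseline levels as covariates. Sex and age appear as exploratory moderators, and the other covariates behind the R2 of 0.3 are not identified.

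**The concern.** A 2x2 analysis tests two averages and one difference of differences. None of these is the combined arm against the control arm. The interaction estimate sets the combination against the single therapies, which is a different question.

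The combination is the main novelty here, and the results are meant to guide a later trial. As written, a statement that it beats control would have to be pieced together from tests of other quantities, or come from a contrast whose form, time point and adjustment are chosen after the data are seen. The stated powers do not describe a comparison of one 20-person arm with another.

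The strata raise a lesser issue. Stratifying makes the arms more alike on sex and age. A model that ignores those factors overstates the standard error to the extent that they predict outcome.

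**Working it through.** **Inputs from Study Design, item 8:** 20 per arm, four arms; alpha 0.05; R2=0.3; tDCS effect d=0.58 on daily smoking and 1.02 to 1.57 on craving (digits running on after 0.58 are read as a citation number). **Assumed, because not given:** two-sided univariate tests, one baseline covariate (80 - 4 - 1 = 75 error df), no interaction, and a range for the AAT effect on daily smoking.

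**1. The plan's own figures.** The adjusted effect is d/√(1-R2) = 0.58/√0.7 = 0.693. A main effect compares 40 with 40, with SE √(2/40) = 0.224 and noncentrality 3.10. The noncentral t (75 df, critical value 1.992) gives power 0.864; the plan says above 0.84. At d=1.02 power exceeds 0.999; the plan says above 0.99. With 20 against 20 the SE is √(2/20) = 0.316, noncentrality 2.19 and power 0.581. Univariately, then, the stated figures fit a main effect and not an arm-versus-control comparison.

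**2. The missing quantity.** Write m11 for AAT+tDCS, m10 for AAT+sham, m01 for AC+tDCS and m00 for AC+sham.
- AAT main effect = ½[(m11+m10) - (m01+m00)]
- tDCS main effect = ½[(m11+m01) - (m10+m00)]
- Their sum = m11 - m00

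The contrast is therefore estimable from the planned model but differs from each tested term. For example, with m00=0, m10=0, m01=1.16 and m11=0, the tDCS main effect is 0.58 and the AAT main effect -0.58, yet combined minus control is 0.

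**3. What the planned tests settle.** The contrast has t = (t_AAT + t_tDCS)/√2. If both main effects are significant and favourable, t is at least 2 × 1.992/√2 = 2.82, so the contrast is significant too. If exactly one is significant, the two tests do not decide the matter.

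**4. How often that happens.** Simulation of 1,000,000 trials; tDCS 0.58; significance counted in the favourable direction:

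| Assumed AAT effect | Exactly one main effect significant | Power of direct contrast | Exactly one significant and contrast not |
|---|---|---|---|
| 0 | 85% | 0.58 | 30% |
| 0.2 | 73% | 0.83 | 9% |
| 0.4 | 45% | 0.96 | 1.5% |
| 0.58 | 23% | 0.99 | 0.2% |

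If both effects are 0.4 (assumed), each main effect has power 0.56 and both are significant in 32% of trials, while the contrast has power 0.85.

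**5. Any single 20-versus-20 contrast.** Power reaches 0.80 at d of about 0.75. At d=0.58 it is 0.44 with R2=0, 0.58 with R2=0.3 and 0.73 with R2=0.5.

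**6. Strata.** Simulation with four balanced strata (two age bands assumed; the cut-points are not given), main effect d=0.58:

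| Share of residual variance due to sex and age (assumed) | Type I error, unadjusted | Power, unadjusted → adjusted |
|---|---|---|
| 1% | 0.049 | 0.865 → 0.867 |
| 2% | 0.048 | 0.866 → 0.871 |
| 5% | 0.044 | 0.870 → 0.881 |
| 10% | 0.038 | 0.876 → 0.898 |
| 20% | 0.028 | 0.888 → 0.927 |

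The gain is about 1 to 4 points at 5-20%, and under half a point at 1-2% before rounding.

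**The case against.** The study calls itself exploratory, says it is not fully powered for the interaction, and names the size of the interaction as what will inform later trials. Combined minus control is an exact sum of two planned estimates, so an analyst could report it without changing the model. The plan also expects the combination to do better than either method alone; on that premise the contrast is well powered and d=0.58, the case where AAT adds nothing, is pessimistic.

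Much of this stands. It limits the point to an unnamed contrast; it does not show that the contrast is planned. The caveat on power concerns the interaction, whereas superiority over control is asserted in both primary aims.

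It can also be said that the group differences in the 2x2x3 model could mean comparisons among the four arms. That reading is possible for cigarettes per day, intent and confidence, so it would be too strong to say that no planned test could ever be read this way. Still, the text names no contrast, and the model leaves out craving, reaction time, P300 and topography.

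On strata, the unidentified covariates might include sex and age, and the protocol reports no past sex differences. The gain may well be small.

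**Conclusion.** The point holds and should be fixed: a hypothesis stated in both primary aims has no explicitly prespecified test. The percentages rest on the plan's tDCS effect of 0.58 and R2 of 0.3, additive effects, univariate two-sided tests and an assumed AAT effect.

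Four stronger readings may tempt a reader, and the documents do not support them.
- **That the trial would reach a false conclusion.** In every tabulated case the combined arm is truly better; the question is simply left open.
- **That AAT and tDCS also lack tests.** If the aims mean factors, the main effects answer them. Only if they mean single arms is there a gap, and the documents do not settle which. The remark in Placebo Arm, item 8 is about risk to controls and is weak evidence.
- **That the stated power is wrong, or concerns tDCS alone.** The attentional-bias figure also rests on an AAT effect (d=1.26). The univariate check agrees with the Aim 1 craving and Aim 2 figures, but the stated power is multivariate and its inputs are not given. One three-outcome case, with d=0.58 on a single uncorrelated outcome, gives 0.72. The multivariate power is therefore neither confirmed nor refuted.
- **That omitting the strata biases the results.** It does not; it makes the tests slightly conservative.

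**What to change.** 1. Keep the planned tests. For each of the eight primary measures at post-training (craving, latency, puff volume, reaction time, P300, cigarettes per day, intent, confidence), add one prespecified model-based contrast of AAT+tDCS versus AC+sham with a 95% confidence interval. Base any statement that the combination beats control on it. For cigarettes per day, intent and confidence, give the 1-week and 1-month contrasts as descriptive estimates.
2. State whether AAT and tDCS in the aims mean the factors, in which case the main effects suffice, or the single arms. If the latter, add the two single-arm contrasts against AC+sham, with Dunnett or Holm adjustment within each outcome at post-training.
3. State that multiplicity across the eight measures is not controlled. If they were independent and each tested at 0.05, the chance of at least one false positive would be 1 - 0.95^8 = 0.34.
4. Add to Study Design, item 8:

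> The stated powers for Aims 1 and 2 are for AAT or tDCS effects and do not apply to a comparison of one 20-person arm with AC+sham; under univariate two-sided assumptions (alpha 0.05, R2=0.3) that comparison has power of about 0.58 at d=0.58 and reaches 0.80 at d of about 0.75.

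Do not use the topography figure of d=0.90 here. It is described as coming from past cue studies and is not evidently a treatment effect.

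5. Include sex and age, coded as in the randomisation, as covariates in every primary model, and state the age bands.

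**Cost.** SAP wording and a few lines of code; no new data. The downsides are a few degrees of freedom; 14 added contrasts (8 post-training plus 3 × 2 = 6 follow-up), or up to 3 × 14 = 42 if single arms are meant; and a less favourable power figure for arm-versus-control comparisons.

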1. Cue Reactivity to personal cues, baseline to post treatment. Attenuation of reactivity to smoking-related cues will be a primary outcome variables for this study. The measures include self-reported cue induced craving, smoking topography measures of latency to light and puff volume, as well as attentional bias measures of reaction time and ERPs to smoking stimuli.

2. Daily Smoking, baseline to post-training and follow up. To examine the impact of AAT + tDCS on daily smoking we will assess each participant's pre- and post-training daily smoking, indexed as cigs/day. We will then re-assess average cigs/per day via follow-up phone call assessments at 2 time points (1-week and 1-month post training).

3. Intent and confidence to quit, Baseline to Post-treatment and follow-up. Participant ratings of Intent to Quit and Confidence to quit will be assessed at baseline and end of treatment to determine if AAT/ tDCS training has a measurable impact on these smoking cessation related measures. To examine prolonged effects of AAT / tDCS, they we be re-assessed at 1-week and 1-month post-training via follow-up phone call assessments.

Secondary:

Sex and Individual Differences, Baseline to Post-training and follow up. Secondary

analyses will probe whether sex and other individual difference variables (e.g., FTND, age) moderate the effect of experimental group on cue-induced craving and attentional bias, smoking topography, daily cig/day and intent & confidence to quit.

4. Provide a description of the following study timelines:

Duration of an individual subject's active participation:

Approx 2 months

Duration anticipated to enroll all subjects:

Approx 19 months

Estimated date for the investigator to complete this study (complete primary analyses):

4/28/2023

5. List the inclusion criteria:

Inclusion Criteria:

- Between the ages of 22 & 65
- Ability to provide written informed consent
- Smoke \geq 5 cigarettes per day
- Expired breath CO \geq 5 ppm at screening
- Ability to attend 10 sessions over a 3-week period, and complete 2 follow-up phone assessments

6. List the exclusion criteria:

Exclusion Criteria:

- Implanted cardiac or brain medical devices
- History of epilepsy or current seizure disorder
- History of brain surgery or skull fracture
- History of a head trauma (losing consciousness >10 min and/or problems with speech or movement because of head injury)
- Latex allergy
- Scalp irritation

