in this experimental study will be replaced. We will examine differential group dropout to assess tolerability of methods. Limited past work leads us to constrain our power analysis to AAT and/or tDCS for each variable, but we expect the synergistic effects of combined AAT + tDCS to be even greater, making these power analyses conservative. However, this exploratory work is not fully powered to detect significant interaction effects. Aim 1. Craving and Attentional bias. Assuming a Cohen's d effect size (ES) of 1.02- 1.57 based on prior literature, a multivariate $\alpha = .05$, and an R2 of .3 from other covariates in the model, we expect to have greater than 0.99 power to detect main effects of tDCS on cue-induced craving. Boggio et al.⁴¹ found an ES of $d=1.13$ for reduction in cue-induced craving via tDCS. Our pilot P300 EEG data from our current study in smokers with schizophrenia shows ES of $d=1.3$. AAT work indicates post-training

attentional approach bias reductions to smoking cues of $d=1.2629$, thus we expect greater than .80 power to detect changes in attentional bias. Aim 2. Smoking topography and cig/day. Based on our past cue studies, smoking topography to multiple cues are of similar magnitude to cue-induced craving ($d=.90$). Further, past tDCS studies of daily smoking outcome show an ES of 0.58100. Thus, with a multivariate of $\alpha=.05$, 20 subjects per group, and an R2 of .3, we expect greater than 0.84 power to detect an effect of tDCS on smoking behavior in both the MANCOVA assessing immediate effects on smoking behavior and the RM-MANCOVA assessing longitudinal effects on cig/day and intent & confidence to quit. Again, tDCS

+ AAT should enhance effects. Aim 3. Smoking prediction. Assuming $\alpha=0.17$ (conservative adjustment for 3 outcome variables) and controlling for other variables contributing an R2 of .3, we will have power greater than .99 to detect an R2 of 0.2422 or larger, in the model predicting smoking topography and cig/day from cue-induced craving and attentional bias change scores.

Research Activities

1. * Provide a detailed description of all research activities (including screening and follow-up procedures) that will be performed for the purpose of this research study. This description of activities should be complete and of sufficient detail to permit an assessment of associated risks.

The PI, Co-I's and Research Coordinators will be responsible for carrying out all the research activities.

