- EEG: The EEG allows us to measure electrical activity of the participants brain. A cap containing sensors will be placed on their head. In addition, sensors will be placed behind the ears, and on the tip of the nose. Gel will be inserted into the cap to connect the sensors to the scalp. The participant will not feel any sensations from these electrodes. While wearing the cap, they will complete the attentional bias training. Afterwards, we will clean as much of the gel from their scalp as possible.
- Cue-reactivity: Cue reactivity involves viewing pictures of the participants personal smoking-related and non-smoking-related pictures and rating how they felt while viewing those pictures. The pictures and the ratings are presented on a computer and some pictures will be projected on the wall.

Visits 3 and 10: During these visits the participant will complete cue-reactivity to their personal smoking and non-smoking cues and smoke cigarettes using a special cigarette holder that will measure how they smoke their cigarette. The participant will be given special instructions on how to light the cigarette and place it into the holder before they smoke. They will be seated comfortably in front of a large computer monitor and view 12 picture trials. Each picture trial will be followed by post-trial ratings. After all the picture trials, a screen will appear informing them that when pictures begin to appear again they may smoke (using the cigarette holder) as much or little as they like, or not smoke at all, it is up to them and watch the pictures. At any point while viewing these pictures they may start or stop smoking.

Visits 4-8: During these visits the participant will go through cue-reactivity while either doing AAT while receiving tDCS (Group 1), doing AAT while receiving sham tDCS (Group 2), doing AC while receiving tDCS (Group 3), or doing AC while receiving sham tDCS (Group 4). The participant will not specifically know which group they are in.

Follow-up: We will call the participants at 1-week and 1-month after visit 10 and ask them how many cigarettes per day they are smoking and ask them the intent and confidence to quit questionnaires.

2. Upload a copy of all materials used to collect data about subjects: (Attach all surveys, interview/focus group scripts, and data collection forms except for case report forms, SCID or KSADS):

Document	Category	Date Modified	Document History
View Environment Listing Sheet(2)	Data Collection	3/2/2023	History

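### The only planned group comparison over follow-up is an RM-MANCOVA that, as normally fitted, drops anyone who misses a single follow-up call

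*Combined protocol and SAP*

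**What the plan says.** Study Design, item 3 places cigarettes per day among the primary endpoints ("Daily Smoking, baseline to post-training and follow up") and does the same for intent and confidence to quit, also through follow-up.

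Study Design, item 8 plans two group analyses that involve cigarettes per day:

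- An analysis of immediate effects: "MANCOVA will test effects on latency to smoke, total puff volume, and cigs/day".
- The longitudinal analysis: "An additional 2x2x3 repeated measures (RM-) MANCOVA will test group differences in cig/day and intent & confidence to quit", run "across time points (post-training, 1-week, and 1-month").

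The two later time points come only from telephone contacts (Research Activities, item 1): "We will call the participants at 1-week and 1-month after visit 10 and ask them how many cigarettes per day they are smoking". Intent and confidence are asked in the same calls.

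On sample size, item 8 states: "Power is based on n=20 high treatment-interest smokers per group, with 4 experimental groups". It claims power above 0.84 for a tDCS effect on smoking behaviour and applies that figure to both the immediate MANCOVA and the longitudinal RM-MANCOVA.

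On incomplete data, the plan says that dropouts are replaced and that dropout is compared between groups for tolerability (Study Design, items 2 and 8). It also says that information collected before withdrawal is kept and used (Risk and Benefits, item 8). It gives no imputation method, analysis population or rule for a missed call.

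**The concern.** A standard repeated-measures MANCOVA takes one row per participant and needs every cell of that row. Here the row holds three outcomes at three times, plus the baseline covariates. A participant who completes Visit 10 and the 1-month call but misses the 1-week call would contribute nothing, although six of the nine outcome values were observed.

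Two things are at stake. The first is precision: the power claim assumes 20 complete participants in each of four groups. The second is bias: if people whose smoking changed less (or more) are harder to reach, a complete-case comparison can misstate the effect on endpoints that the plan calls primary.

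**Working it through.** **1. What one missed call removes.** Values needed per person: 3 outcomes × 3 times = 9, plus baseline. Each call supplies 3 of the 9. In a simulated data set of 80 people, of whom 8 missed only the 1-week call, a nine-column MANCOVA kept 72 rows. It discarded those 8 people's observed post-training and 1-month values. In long format, cigarettes per day alone has 80 × 3 = 240 records. With 8 missing, 232 remain and all 80 people are represented.

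**2. The plan's own power figure.** Inputs from Study Design, item 8: 20 per group, so a main effect compares 40 with 40; alpha 0.05; R² = 0.3 from covariates; and the effect size in "past tDCS studies of daily smoking outcome show an ES of 0.58100". I read this as d = 0.58 followed by a citation number. Two-sided testing is my assumption, since the plan does not say.

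- Noncentrality: λ = N·d² / [4(1 − R²)] = 80 × 0.3364 / 2.8 = 9.61.
- Noncentral F with 1 and 75 df (80 − 4 groups − 1 covariate): power 0.864.
- Normal approximation: √9.61 − 1.96 = 1.14, power 0.873.

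Both agree with a claim of more than 0.84, provided all 80 are complete.

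**3. How many losses the claim tolerates** (same F formula, N = complete cases):

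| Complete cases | Power |
|---|---|
| 80 | 0.864 |
| 76 | 0.846 |
| 75 | 0.841 |
| 74 | 0.836 |
| 72 | 0.826 |
| 68 | 0.804 |
| 66 | 0.791 |

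The claim fails at 74 complete cases, that is, with six people incomplete. The normal approximation is slightly more lenient: 0.842 at 73 and 0.837 at 72.

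**4. What missed calls could do.** The documents give no missed-call rate, so the rates m below are assumptions. Complete cases are 80(1 − m)² if misses are independent between the two calls, and 80(1 − m) if the same people miss both.

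| m per call | Independent: N | Power | Same people: N | Power |
|---|---|---|---|---|
| 5% | 72.2 | 0.83 | 76 | 0.85 |
| 10% | 64.8 | 0.79 | 72 | 0.83 |
| 15% | 57.8 | 0.74 | 68 | 0.80 |

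Power in the independent column is taken at 72, 65 and 58 people (0.826, 0.785, 0.736). Real patterns would probably lie between the two columns.

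**The case against.** Several points on the other side are sound and limit the concern.

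- **Case deletion is not written in the plan.** It follows from the named method when nothing else is specified. That is enough to ask for a change, but it is an inference.
- **The calls are supported.** A reader might assume that they are unpaid and so easily missed. Recruitment Methods, item 4 pays $25 for each, more than the $20 for an ordinary session, and the inclusion criteria require the ability to complete both. This may keep the miss rate low, but it does not make it zero.
- **Not every analysis of daily smoking is exposed.** A reader might infer that a missed call removes someone from all of them. The immediate MANCOVA uses no call data. Aim 3 and the moderator analyses also reach into follow-up, so the RM-MANCOVA is the only planned group comparison over follow-up, not the only use of those data.
- **Replacement may restore numbers.** Nothing limits replacement to losses before Visit 10, and Study Design, item 1 allows 160 enrolled. Nor does the plan say that a missed call makes someone a dropout. For the same reason, adding a further loss at the post-training visit to the table above would not be justified, since dropouts before that point are to be replaced. Replacement would still leave any selection bias in place.
- **The retention statement is not a contradiction.** A reader might set "Research information collected before excusal or withdrawal from the study will continue to be used" against case deletion. That sentence answers a question about withdrawn participants' data. It does not define an analysis set and does not concern someone who only misses a call.
- **The study describes itself as exploratory.** That lowers the stakes, but the plan still attaches a numerical power claim to this analysis.

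**Conclusion.** The concern holds for the follow-up RM-MANCOVA. As normally fitted, that analysis is restricted to participants who answer both calls and have every other value, and the plan contains nothing that would change this.

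The power claim of more than 0.84 is met (0.86) only with nearly complete data and is lost when about six of 80 are incomplete. For assumed miss rates of 5% to 15% per call, power lies between about 0.83 and 0.74 if misses are independent, and between 0.85 and 0.80 if the same people miss both calls. These figures rest on d = 0.58, R² = 0.3, two-sided testing, a univariate 40-versus-40 comparison and no replacement of people who miss calls.

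The possible bias cannot be sized from the documents. It depends on whether reachability is related to smoking change.

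**What to change.** Replace the RM-MANCOVA with a linear mixed model for each of cigarettes per day, intent and confidence. Include AAT, tDCS, their interaction, time, the interactions of these terms with time, the baseline value of the outcome, and sex and age (the stratification factors), with an unstructured covariance over the three times. Include every randomised participant with at least one post-training value.

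Add four statements to the plan:

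1. The model assumes that data are missing at random.
2. A sensitivity analysis under missing-not-at-random assumptions will be reported. The mixed model alone does not remove bias if reachability depends on unobserved smoking change.
3. Either cigarettes per day is the lead outcome, or the three tests are adjusted for multiplicity.
4. Whether a person who completes Visit 10 but misses a call counts as a dropout for replacement.

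The cost is a change of wording and slightly more analysis work. No new data or extra participants are needed. The drawback is that the single joint test of the three outcomes is lost. The gain shown here is in the data retained; no power was calculated for the mixed model.
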